5.5.1 Unscheduled Assessments

Both scheduled and unscheduled assessments, including the assessments at early termination visits, will be considered for planned timepoint summaries based on the above analysis visit windowing rules. All assessments will be presented in data listings.

5.5.2 Multiple Measurements within Visit or Timepoint Windows

In general, in the event that more than one assessment falls within a given visit or timepoint window, the assessment closest to the target study day and time will be selected for the

by-visit or by-timepoint analysis. If two assessments are equidistant from the target study day or nominal time, then the chronologically last assessment will be used. Details are provided in a separate programming conventions document.

All NRS timepoints will be used regardless if the assessment is scheduled or unscheduled.

For safety analyses where the most extreme values should be selected, e.g. overall post-baseline minimum, overall post-baseline maximum, and potentially clinically important values for overall post-Baseline summaries, all non-missing post-Baseline values should be considered, regardless of whether the value is selected for the by-visit summaries. All results will be presented in data listings.

5.6 Missing or Incomplete Date for Last Dose of Study Drug

For subjects with completely missing last dose date, the last dose date will be imputed by the last expected dosing date, defined as the earliest of the following dates: last dose administer date + scheduled dosing interval per protocol, EOT/ET date. For subjects with partial missing last dose date, the imputation will be compared against the last expected dosing date as defined above. Detailed algorithms will be documented in a separate programming specifications document. The missing or incomplete dates will be displayed in the data listings as reported on the eCRF rather than the imputed dates.

5.7 Missing or Incomplete Dates for Concomitant or Post-Treatment Medications

Missing or incomplete medication start or end dates will be imputed for the purpose of determining whether the medications are taken concomitantly (see [Section 11](#) for definition). When the chronological order of medication use relative to the study drug treatment period is unclear due to missing or incomplete date(s), the medication will be considered as concomitant. The imputation algorithms will be detailed in the analysis dataset specification document. The missing or incomplete dates will be displayed in the data listings as reported on the eCRF rather than the imputed dates.

5.8 Missing or Incomplete Dates for Adverse Events

Missing or incomplete adverse event (AE) start dates will be imputed for the purpose of determining whether the AEs are treatment-emergent (see [Section 14.1](#) for definition). When the chronological order of an AE onset relative to the study drug treatment period is unclear due to missing or incomplete date(s), the AE will be considered as treatment-emergent. The imputation algorithms will be detailed in the analysis dataset specification document. The missing or incomplete dates will be displayed in the data listings as reported on the eCRF rather than the imputed dates.

6 DEMOGRAPHICS AND OTHER BASELINE CHARACTERISTICS

Demographics and Baseline characteristics will be summarized for the Safety Analysis Set using descriptive statistics. Variables include age, sex, primary race, ethnicity, height, weight, and body mass index (BMI).

Race will also be categorized by an additional binary category of White vs. Non-White. The eCRF reported age will reflect a subject's age at the Screening visit date; age at screening will be used for all analysis.

6.1 Block Quality Assessments

Assessments of the popliteal block depth (Block Quality Assessment) will be summarized by timepoint (For each hour 0-24 post surgery completion) and treatment group. The assessment consists of three categories, motor, sensory and pain. The categories of motor and sensory will be categorically summarized as None, Some, Normal. The pain category will consist of the intervals based off of a categorical NRS pain intensity score: (0= NRS 0-2), (1=NRS 3-6) and (2=NRS 7-10). Each component of the block quality assessment collected will be listed.

6.2 Missing Severity Assessment for Adverse Events

If will be used for incidence summaries, and the actual values will be presented in data listings.

6.3 Missing Relationship to Study Drug for Adverse Events

If the relationship to study drug is missing for a treatment-emergent AE, a causality of “Related” will be assigned. The imputed values for relationship to study drug will be used for incidence summaries, and the actual values will be presented in data listings.

6.4 Character Values of Clinical Laboratory Variables

If the reported value of a clinical laboratory variable cannot be used in a summary due to, for example, a character string reported for a numeric variable, an appropriately determined coded value will be used in the summary. The coding algorithms will be detailed in the analysis dataset specification document. The actual values as reported in the database will be presented in data listings.

7 SUBJECT DISPOSITION

For subjects who participate in the screening phase but are not randomized (screen failures), their demographics information (including age, sex, and primary race), screen failure reasons (the specific inclusion/exclusion criterion (or criteria) not met or other reasons including the reason due to the COVID-19 public health emergency (PHE) and protocol version will be listed. If a subject is re-screened, then the re-screening subject ID and the final enrollment

status (whether eventually enrolled) will also be displayed in this listing. In addition, the frequency that the screen failure reasons are reported will be summarized. Note that one subject may be deemed ineligible for multiple inclusion/exclusion criteria and may be allowed to rescreen with the permission of the Medical Monitor, provided the screen failure was due to a temporary condition that subsequently resolved.

The number of sites that screened at least 1 subject, number of sites that randomized at least 1 subject, number of subjects screened, and number of unique subjects screened will be tabulated. In addition, the number of subjects enrolled at each site will also be tabulated by Analysis Set and by treatment group and overall.

The number and percentage of subjects who completed the study, discontinued early (all discontinued and by discontinuation reasons including reason due to the COVID-19 PHE), and the reason for discontinuation will be summarized by treatment group using the Randomized Analysis Set. All subjects excluded from the Safety, Full or Per-protocol Analysis Sets, and the reason(s) for exclusion will be listed. The number and percentage of subjects who are excluded from the Per-protocol Analysis Set will be presented in a summary table by reason, and by treatment group and overall.

8 PROTOCOL DEVIATIONS

Protocol deviations will be reviewed periodically over the course of the study. The review process, definition of the deviation categories, and the classification of a deviation as major or minor are detailed in the Protocol Deviation Management Plan. Protocol deviations will also be assessed with respect to relationship to the COVID-19 PHE. A summary of the number and percentage of subjects with major protocol deviations for each deviation category may be presented by treatment group for the Randomized Analysis Set in three ways: all major protocol deviations, COVID-19-PHE related major protocol deviations (if applicable), and non-COVID-19-PHE related major protocol deviations (if applicable). Three data listings of all protocol deviations, COVID-19-PHE related protocol deviations (if applicable), and non-COVID-19-PHE related protocol deviations (if applicable) may be provided.

9 MEDICAL HISTORY

Medical history data will be coded using Medical Dictionary for Regulatory activities (MedDRA) version 24.0. The subject incidence will be summarized for each system organ class (SOC) and preferred term for the Safety Analysis Set. A subject will be counted only once per SOC or per preferred term for the summary.

A listing of the SOC, preferred term, verbatim term for the medical history condition/event, start and stop dates (when available), and an indicator for whether or not the condition is ongoing will be provided.

10 EXTENT OF EXPOSURE AND TREATMENT COMPLIANCE

Summaries of exposure and compliance to study drug will be provided for the Safety Analysis Set.

10.1 Exposure to Study Drug

Exposure in days, the number of doses administered, the number of missed doses and the number of total tablets dosed will be summarized.

10.2 Treatment Compliance

Study drug compliance will be calculated as the number of tablets taken, divided by the expected number of tablets taken*100.

Treatment compliance will be summarized as a categorical variable. The number and percentage of subjects within each of the following compliance levels will be tabulated: <80%, 80 to 120% and >120%.

The number of missed doses will be summarized as a categorical variable: none, at least 1, 2-4, 5-8, 8-12, and >13.

11 CONCOMITANT AND POST-TREATMENT MEDICATION

Prior medication is defined as any medication with stop dates prior to the date of the first dose of study drug. Concomitant medication is defined as any medications that are ongoing at the first dose of study drug or with a start date between the dates of the first and last doses of study drug, inclusive. Post-treatment medication is defined as any medication with a start date after the date of the last dose of study drug. Medications will be coded using WHO Drug Global Dictionary March 2021 or newer version.

The number and percentage of subjects taking prior, concomitant and post-treatment medications will be tabulated separately by each drug class (ATC Level 3) and medication preferred term, treatment group and overall for Safety Analysis Set. Multiple medication usage by a subject in the same category will be counted only once.

Summary of pharmacokinetic concomitant medications will be summarized. Pharmacokinetic concomitant medication is defined as any medications that are ongoing at first dose of study drug or with a start date between the dates of the first and last doses of study drug, inclusive; and taken within two days prior to a pharmacokinetic sample collection. The details of this summary will be discussed in a separate PK analysis plan.

Listings of the prior, concomitant and post-treatment medications will also be provided.

COVID-19 Public Health Emergency (PHE) Related Medications

Concomitant medication analyses described above may also be tabulated and listed by relationship to the COVID-19 PHE (Not related to the COVID-19-PHE vs. Related to the COVID-19-PHE), if applicable.

12 EFFICACY ANALYSES

Unless otherwise specified, all efficacy analyses will be performed using the planned treatment assignments based on the randomization schedule for the Full Analysis Set.

12.1 Efficacy Variables

Primary Efficacy Endpoint

- The mean AUC_{0-24} of NRS of pain intensity scores (using 4 hour window for rescue medications)

Key Secondary Efficacy Endpoints

- Time to first rescue medication use after time 0 (when the first dose on Day 1 is administered)
- Proportion of subjects who were opioid free through 24 hours
- Proportion of subjects who were opioid free through 48 hours
- Proportion of subjects who were opioid free through 72 hours

Secondary Efficacy Endpoints

- The mean AUC_{0-48} of NRS of pain intensity scores (using 4 hour window for rescue medications)
- The mean AUC_{0-72} of NRS of pain intensity scores (using 4 hour window for rescue medications)
- The mean AUC_{0-4} of NRS of pain intensity scores (using 4 hour window for rescue medications)
- The mean AUC_{0-6} of NRS of pain intensity scores (using 4 hour window for rescue medications)
- The mean AUC_{0-12} of NRS of pain intensity scores (using 4 hour window for rescue medications)
- The mean AUC_{24-48} of NRS of pain intensity scores (using 4 hour window for rescue medications)

- The mean AUC_{48-72} of NRS of pain intensity scores (using 4 hour window for rescue medications)
- Amount of rescue medication taken during 0-24, 24-48, and 48-72 hours (individually), 0-48 hours, and 0-72 hours
- Proportion of subjects who did not use rescue medication through 24, 48, and 72 hours
- Proportion of subjects who are pain free (NRS ≤ 2) at 24, 48, and 72 hours
- Number of hours subjects are pain free (NRS ≤ 2)
- Proportion of subjects who were opioid free during 24-48 hours and 48-72 hours
- Global evaluation of study drug just before time of first rescue and at the end of 24, 48, and 72 hours relative to the time 0 (when the first dose on Day 1 is administered)

Exploratory Efficacy Endpoints

- Proportion of subjects with severe pain (defined as an NRS pain intensity score ≥ 7 at any timepoint through 72 hours)
- Foot and Ankle Ability Measure (FAAM)

12.2 Adjustment for Covariates

Unless otherwise specified, there will be no adjustment for covariates.

12.3 Multiple Comparisons / Multiplicity

A fixed sequence method at alpha=0.05 for the primary and key secondary efficacy endpoints will be used to control for multiplicity. The following will be the sequence for testing:

1. 400 mg Q6H compared to placebo on mean AUC_{0-24} of NRS of pain intensity scores
2. 1600 mg QD compared to placebo on mean AUC_{0-24} of NRS of pain intensity scores
3. 400 mg Q6H compared to placebo on time to first rescue medication use after time 0
4. 400 mg Q6H compared to placebo on proportion of subjects who were opioid free through 24 hours
5. 1600 mg QD compared to placebo on time to first rescue medication use after time 0
6. 1600 mg QD compared to placebo on proportion of subjects who were opioid free through 24 hours
7. 400 mg Q6H compared to placebo on proportion of subjects who were opioid free through 48 hours

8. 1600 mg QD compared to placebo on proportion of subjects who were opioid free through 48 hours
9. 400 mg Q6H compared to placebo on proportion of subjects who were opioid free through 72 hours
10. 1600 mg QD compared to placebo on proportion of subjects who were opioid free through 72 hours

The testing procedure will stop once a p-value in the sequence is greater than 0.05. P-values that are less than or equal to 0.05 prior to stopping, will be declared statistically significant; p-values after stopping will be nominal. P-values obtained from the stratified log-rank test stratified by site will be used to for the endpoints that compare the time to first rescue medication use after time 0 by treatment group.

12.4 Examination of Subgroups

Treatment effect will be examined with respect to the primary endpoint using ANOVA described in [Section 13.1.1](#) for the following subgroups:

- Age (<median or \geq median)
- Sex (male or female; reporting on the male subgroup may be omitted if there are insufficient counts)
- Primary race (white or non-white)

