3.5 Determination of Sample Size

The planned sample size is 240 randomized subjects (80 subjects per treatment group).

Assuming a treatment difference in the AUC from 0 to 24 hours is 23 points between the ACP-044 groups and placebo group, and the common standard deviation is 50 points, 76 subjects per treatment arm will provide approximately 80% power to detect the assumed treatment difference using a t-test between each ACP-044 dose arm and placebo at a 2-sided significance level of 0.05. Assuming no more than 5% of randomized subjects will be excluded from primary efficacy analysis, 80 subjects per treatment group will be randomized.

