The hypothesis testing will be performed for the Full Analysis Set using analysis of variance (ANOVA) with treatment group and site as factors in the model. Prior to analysis, missing pain assessments will be imputed before calculating AUC per [Section 5.2.1](#). In addition, the AUC will have the last time point adjusted by as described in [Section 5.2.1.1](#).

The ANOVA results will be processed using the SAS MIANALYZE procedure to yield a combined estimate for treatment effect, standard error, and associated 95% confidence interval (CI) and p-value ([Rubin 1976](#)).

The treatment effect size, Cohen's d, will be presented for both ACP-044 comparisons to placebo using the following formula:

$$\text{Effect Size} = \frac{\text{LS mean difference}}{\text{Standard Deviation}}$$

Where Standard Deviation is approximated:

$$\text{Standard Deviation} = \frac{\text{Standard Error of LS mean Difference}}{\sqrt{\frac{1}{n_1} + \frac{1}{n_2}}}$$

And n_1 and n_2 are the sample sizes in each group. The sign (+ or -) of the effect size will be chosen so that a positive value favors ACP-044.

Summary statistics for the mean NRS pain intensity assessments (before and after single imputation) and the mean of AUC of pain intensity scores, the LS means, the between-group difference in LS mean with the corresponding confidence interval, p-value, and the effect size (Cohen's d) will be presented.

All pairwise treatment group comparisons will be presented.

A line plot of the mean (+/- the SE) NRS pain intensity assessments over time will be presented by treatment group.

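### The subgroup analysis in SAP 12.4 estimates no treatment-by-subgroup contrast, so its p-values cannot show whether the effect differs by age, sex or race

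*SAP*

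**What the plan says.** SAP 12.4 (Examination of Subgroups) states: "Treatment effect will be examined with respect to the primary endpoint using ANOVA described in" Section 13.1.1. It lists three factors: age below or at/above the median, sex, and race as white or non-white. For sex, it allows results for males to be left out when there are too few of them.

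The model referred to, in SAP 13.1.1 (Primary Analysis), is "analysis of variance (ANOVA) with treatment group and site as factors in the model". SAP 12.2 adds: "Unless otherwise specified, there will be no adjustment for covariates". The outputs in 13.1.1 are LS means, the LS mean difference with CI, a p-value and Cohen's d, for all pairwise comparisons. SAP 5.1 sets two-sided 5% tests unless stated otherwise.

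Protocol 9.5.9 leaves subgroup details to the SAP. Neither document contains a treatment-by-subgroup term or says how results in different subgroups are to be compared. The fixed testing sequence in SAP 12.3 covers the primary and key secondary endpoints only.

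**The concern.** Whether the effect differs by age, sex or race is a question about the difference between two within-subgroup effects. A model with treatment and site, fitted inside each subgroup, gives two separate answers and no comparison. The SAP does not use the word separate. But the model has no subgroup factor, and the sex entry speaks of reporting one subgroup on its own, so fitting within subgroups is the natural reading.

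Each within-subgroup test has less power than the overall comparison. When an effect is the same everywhere, it is therefore common for one subgroup to reach p<0.05 and the other not. A reader who compares the two p-values may take that pattern as a difference in effect. Protocol 1.5 calls this a proof-of-concept study, and Protocol 1.6 says a positive result could lead to further development, so a misread subgroup table could affect how a later trial is designed.

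**Working it through.** **Inputs (SAP 3.5).** Difference 23 points; "the common standard deviation is 50 points"; 76 evaluable per arm; two-sided 0.05. The stated result is that 76 "subjects per treatment arm will provide approximately 80% power to detect the assumed treatment difference using a t-test".

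**Step 1: the plan's own figure.** For n per arm, SE = 50 × √(2/n). Power comes from the noncentral t distribution with 2n − 2 degrees of freedom and noncentrality 23/SE.
- n = 76: SE = 50 × √(2/76) = 8.11; noncentrality = 23/8.11 = 2.84; df = 150; power = 80.4%. The stated 80% is reproduced.
- Allowing for 5% exclusions: 76/0.95 = 80 per arm, as stated.

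**Step 2: power within one age half.** A median split leaves about 76/2 = 38 per arm.
- SE = 50 × √(2/38) = 11.47; noncentrality = 23/11.47 = 2.01; df = 74; power p = 50.8%.
- With the residual degrees of freedom of a three-arm model, p = 51.1%, so the choice hardly matters.

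**Step 3: same true effect in both halves.** The halves contain different subjects, so the two tests are treated as independent.
- Exactly one half has p<0.05: 2p(1 − p) = 2 × 0.508 × 0.492 = 50.0%
- Both: 0.508² = 25.8%
- Neither: 0.492² = 24.2%

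**Step 4: how far this depends on the true effect.** The expression 2p(1 − p) cannot exceed 50%, and the planning values sit almost exactly at that peak. With 38 per arm and SD 50:

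| True difference | Power per half | Exactly one half p<0.05 |
|---|---|---|
| 15 | 25.2% | 38% |
| 18 | 34.1% | 45% |
| 23 | 50.8% | 50% |
| 28 | 67.3% | 44% |
| 30 | 73.3% | 39% |
| 35 | 85.3% | 25% |

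With the difference held at 23 and the SD between 40 and 60, the result lies between 42% and 50%.

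**Step 5: unequal splits.** The documents give no sex or race shares, so these are assumptions. At 80:20 the subgroups have 60.8 and 15.2 per arm, with power 71.1% and 23.2%.
- Larger significant, smaller not: 0.711 × (1 − 0.232) = 55%
- The reverse: 0.289 × 0.232 = 7%
- Either direction: 61% before rounding of the two parts. At 70:30 it is 55%, and at 90:10 it is 69%.

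**Step 6: what a direct contrast would give (age).** SE of the difference between the two within-half effects = 50 × √(4/38) = 16.2 points; 95% CI half-width = 1.96 × 16.2 = 31.8 points. With identical effects, a 5% test of this contrast is significant in 5% of trials. If the effects really differ by 23 points, z = 23/16.2 = 1.42 and power is about 29%.

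**The case against.** The strongest reply is that nothing formal is at stake. SAP 12.4 only says that the effect will be examined. It sets no subgroup hypothesis and no rule that a p-value makes an effect present or absent, and these analyses lie outside the fixed sequence. This stands. A reader might infer that the plan will make a false subgroup claim half the time, but the documents do not support that: the 50% is the frequency of a pattern that the SAP never treats as a conclusion. For the same reason, setting it beside the 5% error rate of an interaction test is not a like-for-like comparison of error rates.

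Further points, and what remains of each:
- *The 50% is a ceiling.* This stands. One-half-only is the most frequent outcome at the planned effect but not everywhere: at a true difference of 15, neither half is significant in 0.748² = 56% of trials, and at 30 both are in 0.733² = 54%. Protocol 1.6 calls this the first clinical efficacy study, so 23 points is an assumption.
- *Not every subgroup is small.* This stands. Only the age split halves the sample; the larger sex or race group could hold most of it.
- *The SAP foresees a small male group.* This stands. The unequal-split figures apply to sex only if results for males are reported.
- *The ingredients are there.* A reader could form the contrast from the two within-subgroup estimates and their CIs. This stands in part: the calculation is left to the reader, while ready-made p-values are printed.
- *Table specifications are in a separate document (SAP Section 1).* This limits certainty about what will be displayed, but the method belongs in the SAP.
- *The contrast is imprecise.* This stands, and it governs how the contrast should be read. Imprecision is also what the within-subgroup p-values conceal.

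**Conclusion.** The gap is real and cheap to close. On its natural reading, SAP 12.4 yields subgroup p-values but never estimates whether the effect differs between subgroups. Per dose comparison, an effect that is equal in both age halves gives p<0.05 in exactly one half in up to about 50% of trials, and in about 25% to 50% for true differences from 15 to 35. This rests on SD 50, 38 per arm per half and two-sided 5% tests. The 55% for an 80:20 split rests on an assumed share.

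A reader might go further and infer a threat to the trial's main conclusions. The documents do not support this: the primary and key secondary tests and their multiplicity control do not depend on Section 12.4. The consequence is a possible misreading of an exploratory display.

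**What to change.** Add to SAP 12.4:
1. For each subgroup factor, fit one model on the Full Analysis Set with treatment, site, subgroup and treatment-by-subgroup, run in each imputed dataset and combined as in 13.1.1.
2. From that model, report for each dose versus placebo the within-subgroup differences and the interaction contrast, each with a 95% CI.
3. State that subgroup p-values are descriptive and not to be compared between subgroups.
4. State that the sex interaction is omitted if results for males are not reported.

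A model with continuous age is optional.

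The cost is SAP wording and one additional model per factor, with no new data and no change to sample size. The drawback is low precision: for age, an SE of about 16 points and about 30% power for a 23-point difference in effect. The contrast should therefore be presented as an estimate with its interval, and a non-significant result should not be taken as evidence that the effects are equal.
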